## 12.0 Efficacy Assessments

Assessments that define the quality of response to study treatment will include physical examination, peripheral blood counts, and bone marrow examination. All assessments of response will be made by the investigator in accordance with ELN 2017 criteria ([Döhner 2017](#)). See [Appendix 2](#) for criteria that define each response category.

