### Complete Remission with incomplete blood count recovery (CRi)\*:

CRi requires all aforementioned CR criteria except for residual neutropenia or thrombocytopenia and is defined as:

- Bone marrow blasts <5%
- Absence of circulating blasts and blasts with Auer rod
- Absence of extramedullary disease
- Absolute neutrophil count  $<1.0 \times 10^9/L$  (1,000/ $\mu L$ ) or platelet count  $<100 \times 10^9/L$  (100,000/ $\mu L$ )

\*If patients meet criteria for both CRh and CRi, they should be classified as CRh

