A “3 + 3” dose escalation scheme will be employed in which 1 dose-limiting toxicity (DLT) reported from among the first 3 evaluable patients in a dose cohort will prompt enrollment of 3 additional evaluable patients. More than 1 DLT attributed to LANRA among 6 patients evaluable for DLT would indicate an intolerable dose, thus rendering the most proximate lower dose with either 0 of 3 or 1 of 6 patients with LANRA-related DLTs the MTD in combination with gilteritinib. The starting dose of LANRA is 20 mg QD (Cohort 1, Table 1). To better understand the safety, tolerability, PK, PD, and anti-tumor activity of the study regimen, additional patients (up to a total of 20 per dose cohort) may be allocated to previously cleared dose cohort(s) that are considered safe and adequately tolerated, if there are no available patient slots in the dose level currently being evaluated. The decision to enroll additional patients at a dose level previously cleared by the DEC (ie, enrollment of a “backfill” cohort) will be based on recommendations provided by the DEC coincident with each scheduled DEC convocation. Furthermore, additional patients may be added to a previously cleared dose cohort only if at least 1 of the 3 to 6 patients initially enrolled to that cohort have achieved one of the following ELN 2017-defined response categories: CR, CRh, CRi, PR, MLFS.

Following completion of Phase 1b, an expansion cohort consisting of patients who meet all eligibility criteria will enroll in order to further assess the safety, PK, PD and anti-leukemic activity of the combination at the LANRA MTD/RP2D. Patients enrolled in phase 2 will begin combination therapy with LANRA and gilteritinib on C1D1. Enrollment in Phase 2 will follow a two-stage design for assessment of the primary efficacy endpoint, composite CR (cCR) rate, including those patients who achieve a best response of complete remission (CR) or complete remission with partial hematology recovery (CRh), as defined by European LeukemiaNet 2017 (ELN) response criteria.

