4.2. SAMPLE SIZE

Approximately 100 patients in total are planned for enrollment in the study. Up to 69 patients will be enrolled to phase 1b with the actual number determined by the number of dose cohorts and number of patients in each cohort evaluated for determination of LANRA MTD/RP2D.

Approximately 31 patients are planned for enrollment in Phase 2. The optimal two-stage design to test the null hypothesis that the composite CR rate (CR/CRh) is $\leq 23\%$ (XOSPATA[®] [gilteritinib] US Prescribing Information, 2022) versus the alternative hypothesis, that CR/CRh is $\geq 23\%$ has an expected (average) sample size of 19.26 and a probability of early termination of 0.710. If the study regimen is not effective, there is a 0.025 probability of concluding that it is (the target for this value was 0.025 one-sided). If the study regimen is effective, as defined by CR/CRh = 46%, there is a 0.806 probability of concluding that it is (the target for this value was 0.800). (Calculations made using PASS 2020). After testing the treatment regimen on 12 patients in the first stage (including those treated at the MTD/RP2D in Phase 1b), the trial will be terminated if 3 or fewer patients respond. If the trial enrolls the second stage, additional patients will be enrolled to obtain at least 37 patients treated on the RP2D dose (including at least 6 patients enrolled to Phase 1b and treated at the RP2D). If the total number of patients enrolled to stage 1 and stage 2 who achieve a CR/CRh is ≤ 13 , the study regimen is rejected.

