Complete remission with partial hematologic recovery requires all aforementioned CR criteria except for residual thrombocytopenia and/or neutropenia and is defined as:

- Bone marrow blasts <5%
- Absence of circulating blasts and blasts with Auer rods
- Absence of extramedullary disease
- Absolute neutrophil count > 0.5 x 10⁹/L (500/μL)
- Platelet count > 50 x 10⁹/L (50,000/μL)

Complete Remission with incomplete blood count recovery (CRi)*

Complete remission with incomplete blood count recovery requires all aforementioned CR criteria except for residual neutropenia or thrombocytopenia and is defined as

- Bone marrow blasts < 5%
- Absence of circulating blasts and blasts with Auer rods

- Absence of extramedullary disease
- Absolute neutrophil count $> 1.0 \times 10^9/L$ (1,000/ μ L) or platelet count $> 100 \times 10^9/L$ (100,000/ μ L)

*If patients meet criteria for both CRh and CRi, they should be classified as CRh

Morphological Leukemia Free State (MLFS)**

- Bone marrow blasts $< 5\%$
- Absence of blasts with Auer rods
- Absence of extramedullary disease
- No hematologic recovery required

** Marrow should not be merely “aplastic”, at least 200 cells should be enumerated or cellularity on bone marrow biopsy should be at least 10% of normal

Partial Remission (PR)

PR meets all hematologic criteria of CR:

- Absolute neutrophil count $\geq 1.0 \times 10^9/L$ (1,000/ μ L)
- Platelet count $\geq 100 \times 10^9/L$ (100,000/ μ L) *and*
- Residual bone marrow blast percentage of 5% to 25%
- Reduction of bone marrow blast percentage by $\geq 50\%$ compared with pre-treatment

Stable Disease

Absence of CR, CRh, CRi, PR, MLFS and criteria for PD not met.

Progressive Disease (PD)

Evidence for an increase in bone marrow blast percentage and/or circulating blast count as defined by at least one of the following:

- $>50\%$ increase in bone marrow blasts over baseline (a minimal absolute 15% increase is required in cases with $< 30\%$ blasts at baseline)
- Persistent bone marrow blast percentage $> 70\%$ over ≥ 3 months without at least a 100% improvement in absolute neutrophil counts (ANC) to an absolute level $> 0.5 \times 10^9/L$ (500/ μ L) and/or platelet count to $> 50 \times 10^9/L$ (50,000/ μ L) without transfusion
- $> 50\%$ increase in circulating blasts to $> 25 \times 10^9/L$ ($>25,000/\mu$ L) in the absence of Differentiation Syndrome***
- New Extramedullary disease

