6. STATISTICAL METHODS

Descriptive statistical methods will be used to summarize the data from this study. Unless stated otherwise, the term “descriptive statistics” refers to number of patients (n), mean, medians, interquartile ranges, standard deviation (STD), minimum, and maximum for continuous data and frequencies and percentages for categorical data. The term “treatment group” or “dose group” refers to the dose level of LANRA. Unless otherwise specified, data summaries and analyses described below will be reported by dose group and overall, in Phase 1b. Select data collected during the study will be included in data listings. Unless otherwise noted, the data will be sorted first by dose level/cohort, patient number, and then by date within each patient number.

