6.5. EFFICACY ANALYSIS

Best response (CR, CRh, CRi, PR, MFLS, stable disease [SD], and progressive disease [PD]) will be summarized for the efficacy-evaluable population by frequency distributions and percentages in accordance with ELN 2017 criteria. Patients with no post-baseline response assessments will be considered non-responders. The 95% confidence interval (CI) for estimates of the proportion of patients with CR/CRh will be constructed with exact methods for the binomial distribution (eg Clopper-Pearson intervals). Additionally, 95% CIs for the estimates of the proportion of patients with any CR (CR, CRh or CRi) will be constructed in a similar manner.

Overall survival will be estimated using K-M methodology, including 95% CIs for quartiles. Minimal and maximal survival times will be computed by dose level. Patients alive at last follow-up will be censored at the date of last contact.

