7. CHANGES IN THE PLANNED ANALYSES

The estimated total number of patients was increased from 35 to 100 to accommodate a potential 4th dose cohort in Phase 1b, to increase precision of the type 1 error to 0.025 (1-sided) in Phase 2 for the composite CR endpoint, and to allow for backfill patient enrollment. Eighty percent (80%) CIs for proportions of patients with CR/CRh, those with any CR (CR, CRh or CRi), medians and landmark rates for EFS and duration of response were increased to 95% to reflect the increase in estimated total number of patients.

In light of the Sponsor's decision to terminate the trial at completion of Phase 1b, all analyses, data summaries and listings will be restricted to results from Phase 1b patients only. Phase 2 was not be enrolled.

Following the completion of the protocol specified analyses as specified in this SAP, the sponsor may choose to conduct additional exploratory analyses. Such analyses will be detailed in a separate document.

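### SAP 4.4.4 reverses both blood-count inequalities in the CRi definition, so CRi and the any-CR proportion would be understated if response is derived from the SAP text

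*SAP*

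**What the plan says.** Protocol Appendix 2 defines CRi as marrow blasts below 5%, no circulating blasts or Auer rods, no extramedullary disease, and an ANC below 1.0 × 10⁹/L "or platelet count $<100" × 10⁹/L.

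SAP 4.4.4 repeats the blast and extramedullary criteria, but its count criterion is an ANC above 1.0 × 10⁹/L "or platelet count $> 100" × 10⁹/L. The sentence introducing the definition (CR apart from remaining neutropenia or thrombocytopenia) and the footnote placing CRh ahead of CRi are the same in both documents.

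Protocol 12.0 names who assigns response: "All assessments of response will be made by the investigator in accordance with ELN 2017 criteria". It points to Appendix 2 for the categories.

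SAP 6.5 lists CRi among the best-response categories and adds that "95% CIs for the estimates of the proportion of patients with any CR (CR, CRh or CRi) will be constructed in a similar manner". SAP Section 6 says that "data summaries and analyses described below will be reported by dose group and overall, in Phase 1b". SAP Section 7 records that interval levels for "those with any CR (CR, CRh or CRi), medians and landmark rates for EFS and duration of response were increased to 95" percent. Neither that section nor the revision history mentions a new CRi definition.

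**The concern.** The SAP bullet contradicts the protocol and also its own introductory sentence. CRi is meant to capture remission with incomplete count recovery, yet the bullet asks for a recovered count. A patient with full CR counts satisfies it, and a patient who is both neutropenic and thrombocytopenic does not.

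The text sits in the section that holds the data derivations, so a programmer could reasonably code from it. Appendix A of the SAP relies on independent programming for verification. Two programmers working from the same definition would agree on the same wrong answer.

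At stake are the CRi row of Table 14.2.1 and the any-CR proportion with its interval. With the analysis cut back to Phase 1b, SAP 6.5 gives intervals for only two response proportions, CR/CRh and any-CR, and dose groups are small.

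**Working it through.** **Inputs.** Protocol Appendix 2 and SAP 4.4.4 for CR, CRh, CRi and MLFS; the rule that CRh outranks CRi (both documents). Assumed: CR is assigned before CRh, and CRi before MLFS. All patients below meet the blast and extramedullary criteria. ANC and platelets are in units of 10⁹/L.

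**Who is left after CR and CRh.** CR needs ANC >1.0 and platelets >100. CRh needs ANC >0.5 and platelets >50. A patient who is neither therefore has ANC ≤0.5 or platelets ≤50.

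- Protocol rule (ANC <1.0 or platelets <100): every such patient qualifies as CRi, because 0.5 < 1.0 and 50 < 100.
- SAP rule (ANC >1.0 or platelets >100): such a patient qualifies only if the other lineage is fully recovered, that is ANC ≤0.5 with platelets >100, or platelets ≤50 with ANC >1.0.
- Lost: ANC ≤1.0 and platelets ≤100, with ANC ≤0.5 or platelets ≤50. These patients become MLFS if the marrow cellularity condition is met.

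**The same result on a coarse grid** (protocol → SAP):

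| ANC | Platelets <50 | 50–100 | >100 |
|---|---|---|---|
| <0.5 | CRi → lost | CRi → lost | CRi → CRi |
| 0.5–1 | CRi → lost | CRh → CRh | CRh → CRh |
| >1 | CRi → CRi | CRh → CRh | CR → CR |

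The protocol makes 5 of the 9 cells CRi. The SAP keeps 2 and loses 3. Cells are not patient frequencies.

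**Direction.** A fine grid of 299 × 299 = 89,401 combinations (ANC 0.01–2.99, platelets 1–299) gave:

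- CR unchanged in 39,601 and CRh unchanged in 22,400;
- CRi unchanged in 19,900;
- CRi to MLFS in 7,500;
- no move into CRi.

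A separate 90-point grid that included the exact cut-offs 0.5, 1.0, 50 and 100 gave 30 points where any-CR is lost, none where it is gained, and none where CR/CRh status changes.

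**Size per patient.** One reclassified patient lowers any-CR by 100/n points:

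- n = 69, the Phase 1b maximum (SAP 4.2): 100/69 = 1.4
- n = 20, the ceiling for a backfilled cohort (SAP 2.1): 100/20 = 5.0
- n = 6, an expanded 3 + 3 cohort: 100/6 = 16.7

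**Illustration.** Assume 8 any-CR responders in a cohort of 20; the 8 is not from the documents. Clopper-Pearson 95% intervals:

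- 8/20 = 40.0% (19.1 to 63.9)
- 7/20 = 35.0% (15.4 to 59.2) after one reclassification

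**The case against.** The best counter-argument is that the slip is visible and probably harmless. The introductory sentence shows what was intended. Protocol 12.0 has the investigator assign response under Appendix 2, where the signs are right. The title of Table 14.2.1 refers to ELN 2017 criteria, the SAP plans a response-assessment listing separate from the marrow listing, and SAP 6.5 describes no response algorithm. All this suggests that an assigned category is collected and tabulated, in which case no number changes. Any-CR is not a listed endpoint, SAP 4.1 states that there is no formal hypothesis, and Phase 2 was not enrolled. Backfill eligibility accepts CRi and MLFS alike. The 100/n figures would apply to any single misclassified patient, and 69 and 20 are enrolment ceilings, not efficacy-evaluable denominators.

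Most of this stands as a limit on consequence. It does not remove the discrepancy. The SAP ties duration of response to investigator assessment but says nothing equivalent for best response in 6.5, so the source of Table 14.2.1 remains open. A reader who takes the bullet as a deliberate rule requiring one recovered lineage would still have an undeclared departure from the protocol.

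**Conclusion.** The concern holds. Both inequalities are reversed relative to the protocol, the SAP contradicts itself, and the difference is not declared. If best response is programmed from SAP 4.4.4, any-CR can only stay equal or fall, overall and in every dose group, by 100/n points per affected patient. The same one-way direction holds for the CRi row provided CR is assigned first. Without that order the row could be inflated by patients with full CR counts, but any-CR could not rise, since they already count in it.

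The number of affected patients cannot be estimated from the documents, so the range starts at zero, and it is exactly zero if the investigators' categories are used. CR/CRh, duration of response, EFS, OS and the two-stage rule are unaffected. This is an error in a supplementary descriptive estimate and should be fixed.

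**What to change.** In SAP 4.4.4, change both signs so that CRi reads ANC <1.0 × 10⁹/L or platelets <100 × 10⁹/L, or replace the definition with a reference to protocol Appendix 2. Keep the rule that a patient meeting both CRh and CRi is CRh.

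In SAP 6.5, add one sentence stating whether Table 14.2.1 and the any-CR interval use the investigator's ELN 2017 category or a programmed derivation. If a derivation exists, check its code against the corrected signs.

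The cost is two characters, one sentence and possibly a short code check. No new data are needed.

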## 2.5 Risk Benefit Assessment

### 2.5.1 Gilteritinib-associated Toxicities:

The safety profile for gilteritinib is based on data from 319 patients with R/R AML treated with gilteritinib 120 mg daily, who were enrolled to three clinical trials. The median duration

of exposure was 3.6 months (range 0.1 to 43.4 months). The most frequent adverse reactions following treatment with gilteritinib were increased alanine aminotransferase (ALT) (82%), increased aspartate aminotransferase (AST) (81%), increased blood alkaline phosphatase (69%), increased blood creatine phosphokinase (54%), diarrhea (35%), fatigue (30%), nausea (30%), constipation (28%), cough (28%), peripheral oedema (24%), dyspnea (24%), dizziness (20%), hypotension (17%), pain in extremity (15%), asthenia (14%), arthralgia (13%), and myalgia (13%). The most frequent serious adverse reactions were acute kidney injury (7%), diarrhea (5%), increased ALT (4%), dyspnea (3%), increased AST (3%) and hypotension (3%) ([XOSPATA \[gilteritinib\] Summary of Product Characteristics 2021](#)). Twenty-two (7%) patients permanently discontinued gilteritinib due to an adverse reaction, most commonly increased AST (2%) and ALT (2%) ([XOSPATA \[gilteritinib\] U.S. Prescribing Information, 2022](#)).

Potentially fatal or life-threatening toxicities associated with gilteritinib included Differentiation Syndrome (DS; a syndrome associated with rapid proliferation and differentiation of myeloid progenitors/precursors), reported in 2% of patients; Posterior Reversible Encephalopathy Syndrome (PRES) presenting with symptoms including seizures and altered mental status, reported in <1% of patients; pancreatitis reported in 4% of patients; and treatment-emergent QT interval prolongation in 9% of patients ([XOSPATA \[gilteritinib\] U.S. Prescribing Information, 2022](#); [XOSPATA \[gilteritinib\] Summary of Product Characteristics 2021](#)). Guidelines for the management of these uncommon but potentially serious adverse reactions are provided in [Section 8.1](#). In order to monitor for the occurrence of QT interval prolongation, electrocardiograms (ECGs) will be assessed at Screening, in Cycle 1 on Days 8 and 15, on Day 1 of Cycles 2 and 3, and thereafter, as clinically indicated in accordance with the gilteritinib prescribing information ([XOSPATA \[gilteritinib\] U.S. Prescribing Information, 2022](#); [XOSPATA \[gilteritinib\] Summary of Product Characteristics 2021](#)).

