Diarrhea:	
 
• For Grade 3 diarrhea, uncontrolled with anti-diarrheal medications, interrupt gilteritinib until diarrhea resolves to Grade <math>\leq 1</math>.
 
• Re-start at 80 mg/day if resolved after interruption lasting <math>\leq 14</math> days. If Grade 3 diarrhea does not recur after 2 weeks of reduced dose gilteritinib, escalation to full dose may be attempted at investigator's discretion.
 
• Permanently discontinue gilteritinib for Grade 4 diarrhea, interruption lasting <math>> 14</math> days or recurrence of Grade 3 diarrhea despite dose reduction.
 

Other Grade $\geq 3$ toxicity related to gilteritinib † :	
 
• Interrupt gilteritinib.
 
• Upon recovery to Grade <math>\leq 1</math> or baseline in <math>\leq 14</math> days after interruption, resume gilteritinib at 80 mg/day. For interruptions lasting <math>> 14</math> days or recurrence of Grade <math>\geq 3</math> toxicity despite dose reduction, permanently discontinue gilteritinib.
 

\*DS is associated with rapid proliferation and differentiation of myeloid cells and may be life-threatening or fatal if not treated. Symptoms of DS include fever, dyspnea, pleural effusion, pericardial effusion, pulmonary edema, hypotension, rapid weight gain, peripheral edema, rash, and renal dysfunction. Some cases may present with concomitant acute febrile neutrophilic dermatosis. DS may occur as early as 2 days and up to 75 days after gilteritinib initiation and has been observed with or without concomitant leukocytosis.

\*\*A diagnosis of PRES requires confirmation by brain imaging, preferably magnetic resonance imaging (MRI).

†Since patients will be receiving study treatment daily, chronic, low grade side effects, such as nausea, fatigue, mucositis and diarrhea, while not meeting criteria for treatment modifications, may not be tolerable when experienced for long periods of time. Dose reduction for chronic, low-grade toxicities attributed to gilteritinib may be permitted if these cannot be managed effectively with supportive care.

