## 8.1.2 LANRA

**Table 3: Dose Reductions for LANRA-Associated Toxicities**

Dose Level:	20 mg QD	40 mg QD	60 mg QD	90 mg QD
Dose Reduction for Toxicity	Discontinue	30 mg QD	40 mg QD	60 mg QD

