### 16.3 Assessment of Causality

The investigator will assess the causal relationship between and the occurrence of all AEs using best clinical judgement and taking into consideration the natural history of the underlying disease, concomitant therapies, biological plausibility, the mechanism of action of the study drug and the temporal relationship between the event and the administration of study drug. The investigator should consult relevant safety information and “Guidance for the Investigator” in the IB in formulating his/her assessment of causality.

Each AE should be assessed as either “related” or “not related” to, based on all available information at the time of reporting. Causality assessments may be modified in the context of additional information or details pertaining to the event, after the initial causality assessment is made. An event should be considered related if any of the following criteria are met:

- There is clear evidence to suggest a causal relationship and other possible causal factors can be ruled out.
- There is evidence to suggest a causal relationship and the influence of other factors is unlikely.
- There is evidence to suggest a causal relationship, however, other factors (eg, the patient’s underlying condition or other concurrent AEs) may have contributed to the occurrence of the event.

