## Appendix 1: Definition of DLT

During Part 1 (dose escalation), the DLT assessment period is defined as Cycle 1, Day 1 through Cycle 1, Day 28 and includes the pre-dose assessments for Day 1 of Cycle 2.

NCI-CTCAE Version 5.0 (Common Terminology Criteria for Adverse Events (CTCAE) (cancer.gov) will be used to grade the severity of all AEs. A DLT is defined as any of the following toxicities occurring within the DLT assessment period:

- A nonhematologic toxicity of Grade  $\geq 3$  that is at least possibly related to LANRA *with the exception of*:
  - nausea, and vomiting controlled with antiemetic therapy,  
(**Note:** Grade 3 nausea or vomiting that requires tube feeding, total parenteral nutrition and/or initial or prolonged hospitalization for management will constitute a DLT. Grade 4 nausea or vomiting will always constitute a DLT regardless of management.)
  - infection or infection-related toxicities such as fever/sepsis, febrile neutropenia\*,
  - fatigue,
  - alopecia,
  - isolated electrolyte abnormalities (ie, those without clinical consequences) correctable to Grade  $\leq 1$  within 72 hours with or without supplementation,
  - Grade 3 or 4 Differentiation Syndrome ([Section 8.1](#)) successfully managed with high-dose steroids plus supportive care interventions with resolution within 7 days and without resulting end-organ damage.
- Any toxicity resulting in administration of  $< 80\%$  of the cumulative, Cycle 1 dose for either LANRA or gilteritinib.
  - Note: Administration of  $< 80\%$  of the cumulative Cycle 1 dose for LANRA or gilteritinib for reasons other than toxicity (eg, non-compliance or administrative reasons) will not be considered a DLT but will make the patient unevaluable for purposes of MTD determination and require the patient to be replaced.
- Grade 4 neutropenia or thrombocytopenia lasting  $> 28$  days after treatment onset that is not attributed to active AML and at least possibly related to LANRA.
- Any toxicity resulting in reduction in the dose of LANRA in Cycle 1.

\*In general, infection will not constitute a DLT unless it is assessed as having resulted from unexpectedly prolonged myelosuppression in the setting of  $< 5\%$  blasts in the bone marrow, absence of myelodysplastic changes, and/or absence of AML by flow cytometry in the bone marrow.

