*** Certain targeted therapies, for example, those inhibiting mutant IDH proteins, other kinases or targets may cause a Differentiation Syndrome, i.e., a transient increase in the percentage of bone marrow blasts accompanied by an increase in circulating blasts. In the setting of therapy with such

compounds, an increase in blasts may not necessarily indicate progressive disease. Such instances should be discussed with the study medical monitor on a case-by-case basis.

Composite Complete Remission (cCR)

Achieving either complete remission or complete remission with partial hematologic recovery.

Duration of Response

Duration of response is defined as the time from first qualifying CR (CR or CRh) until relapse or death from any cause, as assessed by study investigators.

Event-free survival (EFS)

Event-free survival (EFS) is defined as the time from C1D1 until treatment failure (i.e., failure to achieve CR or CRh), relapse from CR/CRh or death from any cause.

Dose Limiting Toxicity

A DLT is defined as any of the following toxicities occurring within the DLT assessment period *unless it can be unequivocally determined to be unrelated to LANRA*:

- A nonhematologic toxicity of Grade ≥ 3 that is at least possibly related to LANRA with the exception of:
 - nausea, and vomiting controlled with antiemetic therapy,
(Note: Grade 3 nausea or vomiting that requires tube feeding, total parenteral nutrition and/or initial or prolonged hospitalization for management will constitute a DLT. Grade 4 nausea or vomiting will always constitute a DLT regardless of management.)
 - infection or infection-related toxicities such as fever/sepsis, febrile neutropenia*,
 - fatigue, alopecia,
 - isolated electrolyte abnormalities (ie. those without clinical consequences) correctable to Grade ≤ 1 within 72 hours with or without supplementation,
 - Grade 3 or 4 Differentiation Syndrome successfully managed with high-dose steroids plus supportive care interventions with resolution within 7 days and without resulting end-organ damage.
- Any toxicity resulting in administration of $< 80\%$ of the cumulative, Cycle 1 dose for either LANRA or gilteritinib.
 - Note: Administration of $< 80\%$ of the cumulative Cycle 1 dose for LANRA or gilteritinib for reasons other than toxicity (eg, non-compliance or administrative reasons) will not be considered a DLT but will make the subject unevaluable for purposes of MTD determination and require the subject to be replaced.

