5.1. DLT EVALUABLE POPULATION

Patients will be evaluable for DLT in Part 1 if they meet the following criteria:

- They experience a DLT (as defined in Appendix 1 of the study protocol) after receiving ≥ 1 dose of LANRA during the DLT assessment period (Cycle 1, Day 1 until Cycle 2, Day 1).
- They receive at least 80% of the intended cumulative doses of LANRA and gilteritinib during the DLT assessment period without the occurrence of a DLT.

The DLT Evaluable Population will be used for all DLT data summaries.

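### SAP 4.4.4 narrows the DLT definition without declaring it, while SAP 5.1 still takes its denominator from protocol Appendix 1, so some protocol-defined DLTs can go uncounted in the Phase 1b summary

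*SAP*

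**What the plan says.** Protocol Appendix 1 opens with "A DLT is defined as any of the following toxicities occurring within the DLT assessment period" and then gives four criteria:

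1. Non-hematologic toxicity of Grade 3 or higher, at least possibly related to LANRA, with listed exceptions.
2. Any toxicity that brings the Cycle 1 dose of either drug below 80%.
3. Grade 4 neutropenia or thrombocytopenia beyond 28 days, not due to active AML and at least possibly related to LANRA.
4. Any toxicity that leads to a LANRA dose reduction in Cycle 1.

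SAP 4.4.4 gives the same four criteria but adds to the opening sentence, and so to all of them, the condition "unless it can be unequivocally determined to be unrelated to LANRA".

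SAP 5.1 admits a patient to the DLT Evaluable Population by either of two routes. The first reads "They experience a DLT (as defined in Appendix 1 of the study protocol"; the second is receipt of at least 80% of both drugs without a DLT. It then states "The DLT Evaluable Population will be used for all DLT data summaries". SAP 6.6.2 promises a Phase 1b DLT summary without naming the definition it uses, and the output list in SAP section 10 contains no DLT table. SAP section 7 (changes in planned analyses) and section 8 (revision history) do not mention the DLT definition.

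**The concern.** Two definitions of the same event are in force in one SAP: 4.4.4 says what counts as a DLT, and 5.1 says who is in the denominator. The added condition is redundant for criteria 1 and 3, which already require a possible relation to LANRA. It acts mainly on criterion 2, which the protocol wrote to cover under-dosing of either drug whatever the attribution.

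The condition also has no matching data item in the two documents. Protocol 16.3 records causality in two categories only: "Each AE should be assessed as either “related” or “not related” to, based on all available information at the time of reporting". Nothing there distinguishes an event that is unequivocally unrelated from one that is simply not related, and neither document assigns that decision. The eCRF and the Dose Escalation Committee charter were not available to check.

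DLTs are part of the Phase 1b primary endpoint, and SAP section 7 restricts all reporting to Phase 1b. A DLT summary that can fall short of the protocol's count, or fail to reconcile with the cohort expansions that took place, is a defect in the main result of the trial.

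**Working it through.** **Which criteria the phrase affects**

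| Criterion | LANRA relation already required in Appendix 1? | Effect of the SAP phrase |
|---|---|---|
| 1. Non-hematologic, Grade 3 or higher | Yes | None in practice |
| 2. Under 80% of Cycle 1 dose, either drug | No | Removes events due only to gilteritinib |
| 3. Prolonged Grade 4 cytopenia | Yes | None in practice |
| 4. LANRA dose reduction | No | Rare: protocol Table 3 is headed "Dose Reductions for LANRA-Associated Toxicities", so a reduction normally implies LANRA attribution |

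**Following one patient through the SAP.** The patient receives under 80% of Cycle 1 gilteritinib because of a toxicity judged unequivocally unrelated to LANRA.

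- Appendix 1: DLT under criterion 2. The note making a patient unevaluable covers only reasons other than toxicity, so it does not apply.
- SAP 5.1: in the denominator through the first route, because that route cites Appendix 1. The two routes cannot both be met, so they must be alternatives, as protocol 15.2.1 says explicitly.
- SAP 4.4.4: not a DLT, so absent from the numerator.

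**Effect on the reported proportion.** Each affected patient lowers the proportion by 1/n: 33.3 points at n = 3, 16.7 at n = 6, and 5 at n = 20 (the backfill ceiling).

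| Scenario, six Appendix 1-evaluable patients | Appendix 1 throughout | SAP as written | SAP 4.4.4 definition throughout |
|---|---|---|---|
| (a) One LANRA-attributed DLT plus one affected DLT | 2/6 = 33.3% | 1/6 = 16.7% | 1/5 = 20.0%, or 1/6 once the patient is replaced by one without a DLT |
| (b) One affected DLT in the first three, none in the next three | 1/6 = 16.7% | 0/6 | 0/5 |

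Most of the difference comes from the narrower numerator. The numerator/denominator mismatch alone is small: 16.7% against 20.0% in (a), and nothing in (b). In (b), the cohort was expanded from three to six because one DLT was reported (protocol 4.1), yet the summary would show none.

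**Whether ordinary dose management can reach criterion 2.** In Phase 1b gilteritinib starts on Cycle 1 Day 2. Assuming dosing on Days 2 to 28:

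- Planned dose: 27 × 120 = 3240 mg; 80% of that is 2592 mg.
- For other Grade 3 or higher gilteritinib toxicity, protocol Table 2 calls for interruption and, on recovery within the permitted number of "days after interruption, resume gilteritinib at 80 mg/day".
- Take an interruption starting on Day 15, after 13 full doses (Days 2 to 14), then 80 mg/day to Day 28:

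| Days missed | Cumulative dose | Share of plan |
|---|---|---|
| 1 | 13 × 120 + 13 × 80 = 2600 mg | 80.2% |
| 2 | 13 × 120 + 12 × 80 = 2520 mg | 77.8% |
| 7 | 13 × 120 + 7 × 80 = 2120 mg | 65.4% |

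A two-day hold at mid-cycle, managed exactly as the protocol directs, is enough to meet criterion 2.

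**Which events could qualify.** Liver, diarrhea, QT and pancreatitis events would rarely be called unequivocally unrelated to LANRA. Protocol 2.5.3 names transaminase rises and diarrhea as possible overlaps, 2.5.2.2 reports acute pancreatitis in a LANRA study, and Appendix 4 calls the QT effect of LANRA unknown. One candidate is a Grade 3 or higher creatine phosphokinase rise attributed to gilteritinib alone. Protocol 2.5.1 gives 54% for this reaction on gilteritinib, without a Grade 3 or higher rate, and 2.5.2.2 and 2.5.3 do not name it for LANRA.

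**The case against.** The strongest reply is that nothing is decided by this count. Protocol 4.1 declares a dose intolerable on DLTs attributed to LANRA, and SAP 2.1 says the same. In scenario (a), 1/6 is exactly the count that rule uses, so the phrase can be read as aligning the summary with the MTD rule. This stands as to the MTD. It does not justify the phrase: attribution is already handled in the MTD rule, and the DLT definition did not need narrowing to achieve it.

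Second, an analyst could follow Appendix 1 throughout, since 5.1 cites it, and no miscount would then arise. That is true, but the SAP leaves the choice open, and two programmers could produce different counts from it.

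Third, the affected set may be very small, and the creatine phosphokinase example is not strong. Protocol 2.5.3 includes myalgia among possible overlaps and says its list is not exhaustive. The planned 60 and 90 mg LANRA doses also exceed earlier experience (50 mg for 7 days, or 30 mg long term). Calling such an event unequivocally unrelated would be a bold judgment. This stands and limits the practical size of the problem.

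Fourth, protocol 17.1 allows ad hoc committee meetings to adjudicate individual safety events, which is a possible route for the decision. It does not assign this determination to the committee.

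Fifth, protocol 15.0 lets the SAP modify the protocol's plans and requires an amendment only for major changes to the primary endpoint definition. Whether this change is major is arguable. It still belonged in SAP section 7.

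**Conclusion.** The concern holds. The SAP contains two conflicting definitions of a component of the Phase 1b primary endpoint, and the narrower one is undeclared. Read literally, each affected patient is removed from the numerator but kept in the denominator: 2/6 becomes 1/6, or 1/6 becomes 0/6 in a cohort that was expanded because of a DLT.

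These figures assume one criterion 2 event judged unequivocally unrelated to LANRA, and an analyst who applies 4.4.4 to the numerator and 5.1 to the denominator. The dose route assumes gilteritinib on Days 2 to 28 and an interruption starting on Day 15. How often such events occur is unknown and may be low. No change in the MTD is shown; the effect is confined to the reported DLT summary. The conflict in the text is certain, the miscount is conditional, and the sponsor should correct it before the analysis is run.

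**What to change.** Delete the added phrase from SAP 4.4.4, so that Appendix 1 governs both the count of DLTs and the evaluable population.

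If the exclusion is intended, write it into SAP 5.1 as well, so that numerator and denominator agree; list it in SAP section 7 as a change from the protocol; and state who determines that an event is unequivocally unrelated. A separate column for LANRA-attributed DLTs is optional, and would show the count that the MTD rule uses beside the full protocol count.

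The cost is one phrase removed, or one sentence each in 5.1 and section 7. No new data are needed.
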